### Yes

Baclofen has been FDA-approved for over 40 years for spasticity. It has never been associated with suicidal or homicidal ideation. Please see the previously attached Physicians Desk Reference (PDF) for baclofen. Additionally, in our 15 years of experience with baclofen at our Center no research subjects experienced suicidal or homicidal ideation adverse events.

# **Study Procedures**

### Procedures

All patients who call for treatment will be briefly screened over the phone by a trained intake technician and will be scheduled to come in for an intake appointment. At intake, all patients will be given a psychosocial and physical examination to confirm medical health. These procedures will be performed after signing an informed consent for study screening approved for use by the IRB under the Treatment Research Center overall Center grant protocol. After this brief screening patients who still appear to be eligible for this study will attend a subsequent visit to sign one of the informed consent for this project. All other study procedures will be completed after the study-specific informed consent is reviewed and signed at the first study visit.

Genetics are drawn at this time under [name] "Genetics of Addiction" Center protocol #811705. The TRC has a Genetics Research Bank located at [name] University of Pennsylvania genetic lab with

the purpose of collecting and storing genetic samples from individuals participating in research studies at the University of Pennsylvania Treatment Research Center (TRC). Individuals providing blood samples will have screened and/or participated in various research studies focused on an addictive disorder. These samples will be used to study various candidate genes and/or whole genome comparisons to clinical and demographic data collected as part of the other research studies that the individual has participated. The study proposed in this protocol will be one of the studies that may have overlapping recruitment of participants for the Genetics of Addiction study. As such, the data acquired from the Genetics of Addictions study may be used by the Investigators of this study, according to the protocol and consent of the Genetics of Addiction study. Persons participating in the intake process, for research studies at the TRC or our satellite Media site will be eligible to sign a separate consent for the Genetics of Addiction study. Persons reporting for intake have usually undergone a telephone or in-person screening to see if they are eligible for ongoing studies at the TRC. If they sign consent, participants in the Genetics of Addiction study will have two vials of blood drawn to analyze their genotype, as outlined in the Genetics of Addiction protocol. [name], the Principal Investigator of the Genetics of Addiction study, will therefore make the results of the information obtained from the genetics blood drawn in these studies available to the Principal Investigators of this proposed CURE project. Participants will also be asked to complete a locator form. This form provides space for them to list the names, addresses and telephone numbers of 3 additional contact people that can help us locate them if needed. This will be used to contact participants when staff are unable to reach them using the original contact information given us at the time of consent.

If a patient expresses interest in participating in a described study, the intake worker contacts the study research tech, giving the patient's name and citing his/her interest in the study. The research tech then follows up on the referred candidate by speaking with him/her in person, usually within the same day. The research tech describes the ongoing imaging/ outcome studies in more detail and provides the patient with an informed consent describing the specific screening procedures required for the imaging study and the imaging procedures themselves. The PI will also be available to provide additional detail and to answer questions the patient may have regarding the procedures.

If the patient decides to participate in screening and in imaging, s/he signs a written informed consent. S/he is also given a multiple-choice quiz highlighting the requirements of the study; s/he must answer every question correctly before being allowed to proceed into the study. S/he is also reminded that this consent expresses willingness to participate, but that the subsequent screening process will determine final eligibility. If s/he does not qualify for the study, s/he is paid \$20 for participation in the initial screening procedures.

Generally marijuana and prescription opiates participants and some cocaine participants will call study staff specific extensions after seeing posted advertisements specific for these CURE studies. These participants will be screened by study staff using a substance specific CURE phone screen and will not go through the Treatment Research Center intake process, but instead will scheduled for medical and psychological screenings by our study staff. This process will include the signing of the separate genetics consent under [name] of Addictions study.

Female participants will be asked to initial that they agree to follow one of the acceptable forms of birth control listed in the consent form for the component for which they participate.

#### Screening Procedures: [All Procedures are done for Research Purposes]

1. Urine drug screens (UDS) Urine drug screens for the target drug (using standard cut-offs), will be the primary outcome measure. These will be obtained twice weekly during the 12- week active treatment period, and once weekly during the 12-week follow-up period. They will be processed as part of the VA collaboration. A 10-panel dipstick urine drug screen and a urine pregnancy test (females) will be done prior to each naltrexone injection for prescription opiate participants during the first 3 treatment months and may be done once a month during follow-up as well or if the VA is able to add the 2 additional tests (buprenorphine and oxyContin) to their urine drug screen then the VA option may be used during follow-up. Also, a 10-panel dipstick urine drug screen will be done once for all the studies as part of the screening process. For prescription opiate participants additional 10-panel dipstick urine drug screens may be done for detox, encouragement and safety reasons.

2. Sexually-transmitted infections/HIV testing. Our addicted patients are at high risk for HIV, both through drug-related activity (sharing crack pipes), and through unprotected sexual activity occasionally in the context of drug use. Our brain variables (hyperresponse to the promise of reward; poor inhibition of impulses toward drug and sexual reward) would be expected to predict these secondary outcomes. We will test for HIV at baseline and at 24-week follow- up.

3. Genetics. Blood samples for DNA analysis will be obtained from each participant during initial screening. [name] lab will provide the genetic analysis. Genomic DNA will be extracted from anticoagulated venous blood samples using a standard salting out method [96]. Genotyping of the DRD4, DAT VNTR and OPRM1 will be performed using standard methods as described previously [97-99]. DRD2 and COMT genotypes will be determined using the Applied Biosystems Inc. (ABI) Assays-on-demand (ABI, Foster City, CA, USA) SNP genotyping assay as per manufacturers protocol. Genotyping quality control steps for all markers will include Hardy-Weinberg equilibrium determination and genotyping of 20% duplicates for each marker. (Collected under [name] IRB approved genetic protocol #811705.)

4. Baseline psychosocial intervention. The Coping with Craving Program [100] is a manually guided behavioral treatment developed by [name] and [name] in the 1990s with NIH support. It has been widely distributed by NIH/NIDA, has been translated into several languages, is easily modified for a target drug of abuse, and has shown treatment benefit [101]. It demonstrates sensitivity to baseline differences (good prognosis vs. poor prognosis) in our patients --- a useful feature for the current prediction proposal. In the approach, patients are asked at the outset of a session to recount a craving episode in the presence of a trained clinician, and they are then taught a Tool of the Day in an effort to help them reduce the craving/arousal. The tools include 1) practicing relaxation training to counter arousal; 2) delaying use of cocaine while engaging in behavioral alternatives; 3) recalling explicit negative consequences of cocaine use, and positive consequences of abstaining from cocaine use; 4) using negative and positive imagery related to consequences of cocaine use; 5) using mastery imagery to personify craving and counter cocaine use; and 6) replacing cognitive distortions (thought traps) related to drug use, with logical, rational thinking. Forty-five minute sessions will be scheduled twice weekly during weeks 1-12; the treatment will be provided by skilled practitioners (Masters and Doctoral level) who are already highly familiar with the methods.

5. Incentives for attendance, scanning and completion of follow-up. Based upon prior experience with clinical outcome and imaging studies, we provide clear incentives for attendance, for completion of scanning, and for completion of the several assessments at scheduled follow-ups. These incentives have been critical for preventing data loss and attrition [102, 103]. Recent use of the fishbowl strategy (patients draw vouchers that can be redeemed at a nearby CVS) had a strong impact on retention in our cocaine outpatient trials, improving retention to nearly 90% at 8 weeks.

6. Screening and Research Assessments: [All Procedures are done for Research Purposes]

SCREENING: Addiction Severity Index (ASI) [104]: The ASI is a structured interview yielding composite scores reflecting the patient's functioning in seven areas: drug use, alcohol use, medical, employment, psychiatric, legal, and family- social problems. Composite scores are computed in each area to provide an indication of recent problem severity. This instrument has been shown to have good reliability and its concurrent and predictive validity have been demonstrated.

PTSD Checklist Civilian (PCL-C): The PCL is a standardized self-report rating scale for PTSD comprising 17 items that correspond to the key symptoms of PTSD.

Edinburgh Handedness Inventory [106]: This 10-item questionnaire reliably assesses the dominance and preference of the individuals right or left hand in daily activities.

Mini International Neuropsychiatric Interview (MINI) [107]: The MINI is a 15-30 minute structured diagnostic interview providing DSM-IV Axis I diagnose, and will be used to screen for psychosis, bipolar disorder, current

major depression and suicidal risk, and to assess for Antisocial Personality Disorder. A clinician trained and certified to administer this instrument.

Wechsler Abbreviated Scale of Intelligence (WASI) [108]: As a brief and reliable measure of intelligence for both clinical and research settings, WASI is a valid screening measure of verbal, performance, and general intellectual ability. A trained diagnostician will administer the two-subtest form (vocabulary and matrix reasoning) during screening that yields a Full Scale IQ score, which serves as a good estimate of the individuals cognitive functioning.

Parent-Child Relationship Inventory (PCRI): The PRCI is a 78-item inventory completed by parents, which gives a clear, quantified description of the parent-child relationship and identifies specific areas in which problems may occur.

RESEARCH ASSESSMENTS/ QUESTIONNAIRES: [All Procedures are done for Research Purposes]

Beck Anxiety Inventory (BAI) [109]: The BAI is a 5-minute self-administered 4-point, 21 item questionnaire, which examines common symptoms of anxiety. Though patients with anxiety disorders will be excluded, this instrument can monitor symptoms, which fall below diagnostic levels. BAI will take approximately 5 minutes to complete.

Beck Depression Inventory (BDI) [110]: The BDI is a self-administered 4-point, 21 item questionnaire probing cognitive and somatic symptoms of depression. Though patients with major depression will be excluded, this instrument can monitor depression symptoms, which fall below diagnostic levels. BDI will take approximately 5 minutes to complete.

Craving Scale: a 10 question scale that asks to what degree a person is feeling craving, high-like feelings, good feelings, withdrawal and how the person feels using on a 0 to 9 scale.

Marijuana Craving Scale: Is a 12-item self-report instrument that assesses marijuana craving along four dimensions - compulsivity, emotionality, expectancy, and purposefulness.

Cannabis Withdrawal Assessment Scale [112, 113]: This clinician- administered questionnaire probes for subjective reports on marijuana withdrawal symptoms, such as changes in mood, appetite and sleep (Component 2 only).

Clinical Opiate Withdrawal Scale (COWS) [115]: COWS is a clinician-administered instrument that assesses the degree of opiate withdrawal examining eleven common opiate withdrawal signs or symptoms (Component 3 only.)

Medication Compliance/Pill Count: A form that records pill prescribed and pills taken for marijuana and injections received for prescription opiates (yes/no) and dates.

HAM A/D: The Hamilton Anxiety Rating Scale (HAM-A) is a widely used and well-validated tool for measuring the severity of a patient's anxiety. The Hamilton Depression Rating Scale (HAM-D) has proven useful for many years as a way of determining a patient's level of depression before, during, and after treatment.

Bradycardia Assessment: Bradycardia is a slower than normal heart rate. Nurses will take this measure at Weeks 0, 3, and 12. A score from 0-7 will be entered.

Daily Diary and Rating Scale: A daily diary will be used to record use of all substances and intensity of craving. This form will be collected on a weekly basis.

Modified Cigarette Evaluation Questionnaire (mCEQ) [117]: The mCEQ assesses the degree to which subjects

experience the reinforcing effects of smoking. It is a validated and reliable measure with multi-item domains on smoking satisfaction, psychological reward and aversion, as well as the single-item assessment on enjoyment of respiratory tract sensations and on craving reduction.

Positive and Negative Affect Scale (PANAS) [119]: This is a brief, computerized self-report rating scale that examines the degree to which the subject is experiencing positive and negative moods in the moment. The scales will be administered immediately before the imaging and the neuropsychological tasks, to control for mood/affective state during task performance.

Risk Assessment Battery (RAB) [120]: RAV is a self-administered questionnaire to assess HIV risk behavior in the previous 6 months, and consists of sexual- and drug- risk subscales.

Menstrual Cycle Questionnaire (MCQ): An instrument developed by our lab for the purpose of collecting data on Menstrual Cycle Phase and PMS/PMDD symptomatology to examine their impact on addiction/smoking behavior. Physical and emotional symptoms of PMS are separated and a history of menstrual cycle characteristics are collected.

Toronto Alexithymia Scale (TAS): The TAS is a 20-item instrument that is one of the most commonly used measures of alexithymia. Alexithymia refers to people who have trouble identifying and describing emotions and who tend to minimize emotional experience and focus attention externally.

Quality of Life and Functioning (MOS- SF) [121]: The MOS-SF-12 is used to measure general physical and mental health function. The SF-12 has good reliability and validity.

Mother -to-Infant Bonding Scale: An 8-item self-report research instrument that uses a 4-point Likert-style scale to assess the feeling of a mother toward her infant. The questionnaire was modified to probe the mother's feelings toward her child during the first few years of the child's life instead of the first few weeks.

Shiffman-Jarvik Smoking WD questionnaire (S-J) [122]: A widely used self-report 25-item questionnaire, SJ has been developed to assess WD symptoms. This will be administered pre-and post cue exposure to determine whether WD has accrued over the time in the scanner.

WASI Working Memory Index (WMI): Requires working memory processes applied to the manipulation of orally presented verbal sequences. Tests the ability to temporarily retain information in memory, by performing some operation or manipulation with it, and produce a result. Involves attention, concentration, mental control, and reasoning. Essential component of other cognitive higher order progresses.

Smoking History Questionnaire (SHQ): This is a laboratory-developed questionnaire that includes the Fagerstrom Test for Nicotine Dependence [123], and assesses smoking topography and severity of nicotine dependence.

Time-Line Follow-Back (TLFB) [124]: The TLFB will be used at baseline and weekly assessment to measure alcohol and drug use. The TLFB will cover the 30 days prior to the study (at baseline) as well as the seven days (at weekly assessment) during the study.

Within Session Rating Scale (WSRS) [125]: This scale is used to assess craving and other subjective responses, and has been adapted to measure cocaine, marijuana and opiate craving. WSRS is administered on three occasions on each scan day: prior to scan, after cue-exposure, and after craving modulation attempts.

Cannabis Withdrawal Scale (CWS): This is a modified version of a 19-item scale used to measure the intensity of marijuana withdrawal symtoms since last use. This will be administered on scan days to marijuana participants only.

LABORATORY ASSESSMENTS: [All Procedures are done for Research Purposes] Genotyping: Blood sample will be collected for genotyping. Genomic DNA will be extracted from blood samples by standard methods.

Urine Toxicology: Baseline and weekly urine drug screen will be collected and submitted for analyses at the PVAMC. The urine drug screen will be used to detect the following drugs: amphetamines, barbiturates, benzodiazepines, cocaine, marijuana, opiates, methadone and PCP. It will also be used to test for cotinine at Scan Day 1, Scan Day 3 and Scan Day 4 (for prescription opiates all cotinine tests will be done either on or prior to each of the injection days). This may also be done for the Baby Schema pilot on scan day.

Saliva Drug Test (SDT; Drager Drug Test 5000) - Saliva samples may be collected to determine recent use of illicit substances, including amphetamine, methamphetamine, cocaine, opiates, cannabis, and benzodiazepines. The test is carried out in four straightforward steps. First, the protective cap is removed from the oral test collector and the test cassette is handed to the donor. The donor then places the collector inside his or her mouth and, by using a sideways motion between the cheek and gum, takes an oral fluid sample. As soon as sufficient fluid has been gathered, the built-in indicator will turn blue and the test cassette can be handed back to the study personnel. The study personnel will then transport the sample to the Analyzer to obtain the results of the test. This will only be done for the marijuana component. This is being done since it is able to determine that substances were used within a recent window (a couple of hours to a few days depending on the substance) and can be used as an outcome measure for marijuana since this test is more sensitive to recent marijuana use and will not be positive for prior use that still shows as positive in an urine sample.

ADDITIONAL MEASUREMENTS (Safety): [All Procedures are done for Research Purposes]

Adverse Events (AE) Assessment: A semi-structured interview is designed to assess and track the onset, course, and severity of adverse events. AE will be collected and recorded at each weekly visit. Type, severity, relatedness to standard treatment, action taken, and outcome will be recorded. Designations of mild, moderate, and severe will be used to assess severity of any adverse effects. All locally relevant Internal Review Board (IRB) regulations and practices concerning adverse event reporting will be followed.

Concomitant Medications: Concomitant medications are recorded during the study period on a weekly basis.

Medical History and Physical Exam: After obtaining informed consent, a complete medical history and physical exam will be conducted by a physician or a nurse during screening.

Treatment Services: All treatments for substance use disorders and other conditions received during past seven days will be obtained by way of self-report during the second weekly meeting.

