Study Specific Background Prescription Opioids Prescription opioid abuse and dependence (POD) is illegal use of prescription opioids obtained on the black market for non-medical purposes. POD is a significant and growing public health problem [53, 54] both nationwide [55-57] and in Pennsylvania [23, 58]. Though the incidence of POD in the US is more than four times higher than heroin abuse and dependence [37], less is known about the clinical characteristics of POD than heroin dependence [59]. Relapse to drug use is a hallmark of opioid addiction. The harm of relapse in POD is compounded by the risk of transition to heroin [60]. The main clinical priorities in POD management are predicting vulnerability to relapse and predicting and monitoring patients' response to pharmacological treatment. Presently, both domains rely on history, physical examination and urine toxicology that are time-consuming and susceptible to subjective distortions [61, 62]. Studies indicate that cue-induced drug craving and impaired ability to consciously regulate ones own behavior are markers of vulnerability to relapse in SUD patients [63]. The brain fMRI correlates of these behavioral domains have been identified and found to be potentially clinically useful as markers of relapse vulnerability and response to treatment [64-66], especially when integrated with behavioral (i.e. relapse, cue-induced craving and decision-making), genetic and pharmacokinetic variables. Such an approach has been termed pharmaco-MRI (phMRI) [67-69]. The two main advantages of phMRI are increased power and additional information about mechanisms of action of the study intervention, which are not available with conventional clinical trials. Despite evidence of utility in other SUDs, phMRI has not yet been applied to POD. The primary objective of this proposal is to develop clinically useful neurobiological markers of vulnerability to relapse in POD, using a phMRI approach.

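### In the prescription-opioid cohort, the VA urine panel behind the primary outcome is not shown to detect oxyContin or buprenorphine, and about 18 of the 20 Objective 1 urines have no other scheduled test for them

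*Combined protocol and SAP*

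**What the plan says.** - **Outcome.** Screening Procedures, item 1 (Urine drug screens): "Urine drug screens for the target drug (using standard cut-offs), will be the primary outcome measure". On schedule and laboratory: "These will be obtained twice weekly during the 12- week active treatment period, and once weekly during the 12-week follow-up period" and "They will be processed as part of the VA collaboration".
- **VA panel.** The Urine Toxicology entry under Laboratory Assessments says the VA screen detects "amphetamines, barbiturates, benzodiazepines, cocaine, marijuana, opiates, methadone and PCP". These are eight classes, and neither oxyContin nor buprenorphine is named. Cotinine is added on certain days.
- **Dipstick in treatment.** Item 1 says that a 10-panel dipstick "will be done prior to each naltrexone injection for prescription opiate participants during the first 3 treatment months". The naltrexone dosing schedule gives three injections: week 1, then two more about 30 days apart.
- **Follow-up.** The dipstick may be done monthly. Alternatively the VA screen may be used "if the VA is able to add the 2 additional tests (buprenorphine and oxyContin) to their urine drug screen". The VA alternative is mentioned for follow-up only.
- **Scoring.** The Analysis Plan scores each urine as a yes/no for the cohort's drug, using the last ten weeks of treatment for Objective 1 and the weekly post-treatment urines for Objective 2. No section says that a dipstick result enters the outcome.
- **Purpose of the cohort.** The prescription-opioid background states: "The primary objective of this proposal is to develop clinically useful neurobiological markers of vulnerability to relapse in POD".

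**The concern.** This cohort is defined by non-medical use of prescription opioids. The protocol singles out two such drugs as not yet on the laboratory screen that supplies its outcome. The prescription-opioid background itself notes that buprenorphine is open to illicit diversion.

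Any missed use would not scatter evenly over urines. It would follow the patient's drug of choice, so someone using only an untested opioid could be negative visit after visit, and the random intercept would read that run as abstinence. Relapse would be under-counted. If drug choice is unrelated to the brain measure, the estimated association would be pulled toward no effect. If the two are related, the direction of the bias is unknown.

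**Working it through.** **1. The plan's own counts.** Objective 1: 2 urines per week × 10 weeks = 20, as stated under Primary outcome variables. Objective 2: 1 × 12 = 12, as stated. Opioid cohort: 72 of 216, or one third.

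**2. What the dipstick adds.** The VA list has 8 classes. Adding the 2 extra tests gives 10, which matches a 10-panel dipstick. The dipstick's contents are not listed, so this match is an inference.

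**3. Scheduled coverage in treatment.** Injections fall in week 1 and at about days 30 and 60, roughly weeks 5 and 9. The outcome window is weeks 3 to 12, so the first dipstick precedes it and two fall inside.
- Dipsticks count toward the outcome: 20 − 2 = 18 of 20 urines (90%) have no scheduled test for these drugs.
- Dipsticks do not count: 20 of 20.

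**4. Coverage in follow-up.**
- No optional dipstick: 0 of 12 urines covered.
- Monthly dipstick: about 3 of 12.
- VA adds both tests and uses them weekly: 12 of 12.

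**5. Size within the cohort.** Let m be the share of opioid-positive urines that contain only these two drugs and are missed. The documents give no figure, so m = 25%, 50% and 75% are assumptions. Observed rate = p(1 − m). The value p = 0.35 is the midpoint of the plan's 0.2 to 0.5.
- 0.35 × 0.75 = 0.26
- 0.35 × 0.50 = 0.18
- 0.35 × 0.25 = 0.09

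If the two scheduled dipsticks count in treatment, sensitivity is 1 − 0.9m, and the rates become 0.35 × 0.775 = 0.27, 0.35 × 0.55 = 0.19 and 0.35 × 0.325 = 0.11.

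**6. Size in the pooled analysis.** The plan's detectable odds ratios for Objective 2, 1.41 and 2.04, serve as a scale. The matching sentence for Objective 1 is incomplete in the text available.

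Reproduction of these figures: β² = (z₀.₉₉₃₇₅ + z₀.₈₀)² × [1 + (12 − 1)ρ]/12 ÷ [n p(1 − p)], with n = 144 × 0.925 = 133.2 (half of the 15% loss).
- At p = 0.5 and ρ = 0.3: 11.15 × 0.358 ÷ 33.3 = 0.120, so the odds ratio is 1.41, as stated.
- The upper figure is approached only at p = 0.1 and ρ = 0.5 (2.03). At the stated lower rate of 0.2 it is 1.70. This is a side point, and 2.04 is used below only as a stated value.

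Attenuation: true probability π(x) = expit(logit 0.35 + ln(OR)·x), with x standard normal. With one third of subjects affected, the pooled observed probability is π(x)(1 − m/3). A marginal logistic model in x is fitted to it with no cohort term, since the planned models name the brain predictor as the only explanatory variable.

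| m | factor 1 − m/3 | OR 2.04 becomes | OR 1.41 becomes |
|---|---|---|---|
| 25% | 0.917 | 1.96 | 1.39 |
| 50% | 0.833 | 1.89 | 1.37 |
| 75% | 0.750 | 1.83 | 1.35 |

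Hand check at m = 50% for 2.04: π(0) = 0.350 and π(1) = 0.524. Multiplied by 0.833 these are 0.292 and 0.436, with odds 0.412 and 0.774. The ratio is 1.88, close to the fitted 1.89.

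**The case against.** The case on the other side has real force on several points.

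- **Follow-up may be fully covered.** A reader might infer that the two drugs are tested monthly at best in follow-up. The text does not support that. The weekly follow-up urines go to the VA, and if it adds both tests all 12 could be covered. This stands: follow-up is unresolved, not shown to be deficient.
- **Non-detection is not stated.** A reader might infer that a patient using oxyContin is certain to be scored drug-free, or that the outcome does not measure its target drug. The panel includes opiates and methadone, and the documents do not say whether the opiates test reacts to oxycodone. The Urine Toxicology entry may also be an incomplete specification, since it says weekly where item 1 says twice weekly. The primary outcome section speaks of illicit-positive urines, so another drug could turn a urine positive, although that would not measure the target drug. What can be said is that detection is not shown.
- **Unscheduled dipsticks exist.** They are allowed for detoxification, encouragement and safety, and to release delayed payments, so 2 of 20 counts scheduled tests only. This stands, but such tests depend on the patient's situation and, for payments, on earlier positive urines. They are no substitute for uniform testing.
- **Only one third of subjects are affected.** Applying the loss to 1.41 and 2.04 as if every subject were in the opioid cohort would overstate it, because those are pooled three-cohort figures. The pooled values above are the relevant ones, and they are moderate.

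None of this supplies a routine test for the two drugs on the treatment-phase urines.

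**Conclusion.** The concern holds for the treatment phase. In the opioid cohort, about 18 of 20 Objective 1 urines (20 of 20 if dipsticks do not count) have no scheduled test for two drugs that the protocol itself regards as additional to the VA panel. For Objective 2 the plan leaves coverage open, from none to all.

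The effect on the cohort's recorded use rate could be large, and the effect on a pooled odds ratio is modest. Both sizes rest on assumed missed shares. The odds ratios also assume a base rate of 0.35, complete non-detection of those urines, drug choice unrelated to the brain measure, opioid patients remaining one third of the sample, and a marginal model, whereas the plan specifies a random intercept.

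The documents do not support the wider conclusion that the cohort's outcome fails to measure opioid use, nor any claim about the cocaine and marijuana cohorts. The change is a cheap improvement. It needs to be made before collection, because use that no test looked for cannot be recovered later.

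**What to change.** Amend item 1 (Urine drug screens) for the opioid cohort:

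1. Test every outcome urine, twice weekly in treatment and weekly in follow-up, for oxyContin and buprenorphine. Use the 10-panel dipstick already in use, after confirming that it covers both, or the VA panel if it adds both tests.
2. Score a urine opioid-positive if either the VA panel or that scheduled test is positive for any opioid, and list the opioids that count.
3. Keep ad hoc dipsticks (payment, encouragement, safety) out of the outcome, so that detection does not depend on a patient's earlier results.
4. Use the weekly Time-Line Follow-Back only in a sensitivity analysis. In the primary outcome it would mix self-report unevenly into a urine-defined endpoint.
5. Reconcile the weekly wording under Urine Toxicology with the twice-weekly schedule in item 1.

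Cost: consumables, at most 32 urines × 72 patients = 2,304 dipsticks before attrition, plus the time to run and record them. No new visit or sample is needed. The compensation section already provides for a dipstick on regular-visit urine, though only to release payment, so the wider use must be written in.
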